3.9. Data collection

Data are collected by immunisation providers as part of the routine programme. While data on the number of vaccines administered and denominators (i.e. not including data on consent) will be submitted centrally at the end of November 2016, December 2016, January 2017 and February 2017 only the final data submission in March 2017 will provide school-level data and data on consent as well as uptake.

Many areas use a spreadsheet generated by PHE which records individual level data for local management and enables data to be cumulated to the different levels required (e.g. school, local authority) and includes data on consent. These different

cumulative levels can be submitted as required, without the inclusion of individual-level data.

School-level data by school year are routinely submitted to PHE. We will obtain final school-level data from PHE at the national level in March 2017. These data will then be linked with the allocation list for analysis using the School Unique Reference (Figure 2). We will ask providers to submit an interim school-level data extract (e.g. in November) to enable the analysis to be fully planned (i.e. statistical analysis code written) ahead of the availability of final data. This will be important to enable the timely production of results which can then inform next year's programme, however it will not be compulsory if an area is not able to provide these interim data. This analysis will be seen only by a quorum of the investigators and they will not be results released to the wider study team or beyond so as not to impact on the final uptake data. No individual-level data or Personal Identifiable Information will be collected.

Data on characteristics of the schools will be obtained from publically available sources and linked to the immunisation database. This will include data from gov.uk, Compare school and college performance website^v on characteristics such as the proportion of children on free school meals, pupils with English not as the first language, religious denomination of the school and type of school. The postcode of schools will be linked to Index of Multiple Deprivation (IMD) data to obtain a deprivation indicator, quintile or decile ranking, for the school location.

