3.10. Data analysis

Analysis will be undertaken by the PHE Behavioural Insights Team working with the Statistic Unit, PHE National Infection Service. Our main analysis will be by intention to treat allocation for the primary and secondary outcomes. We will use logistic regression to investigate the main effect of the interventions and their interaction. The model also will include provider, local authority and school effect to take into account extra variation that was not explained by intervention and other confounder variables. In the models, we will also investigate the impact of secondary factors such as school-year (to determine if there's any greater impact for those that have not previously

received an invitation letter) and inequalities (e.g. IMD quintile, proportion of children eligible for free school meals, proportion of children not with English as first language).

We will also undertake a per-protocol analysis of the primary and secondary outcomes, including in the analysis only those schools in trial arms 1 and 3 who implemented the request to send a reminder message with high fidelity to the request and those schools in trial arms 2 and 4 who did not send a reminder request. While the intention to treat analysis will be a composite of the effectiveness of reminders and the prevalence of SMS/email systems, the per-protocol analysis will enable these components to be disentangled.

We will analyse the invitation letters used in non-trials areas by coding the letters using the Theoretical Domains Framework (TDF). This will enable us to assess their behavioural-insight framing and fidelity to the new template letter. We will analyse whether those areas that used a letter similar to the new template had i) higher uptake and ii) greater change in uptake from to last year, compared to areas that used a dissimilar letter.

4. Study sponsorship and approvals

This study has been reviewed by the PHE Research Ethics and Governance Group to gain approval for PHE to act as the study sponsor.

Health Research Authority (HRA) approval has been sought, which includes ethical (opinion provided through UK Health Departments' Research Ethics Service), governance and legal review. (HRA/ethics number xxxxxxxx).

The trial has been registered on clinicaltrials.gov, trial number xxx.

5. Main risks and mitigation

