5.1. Timelines

The main risk to the successful implementation of this trial is meeting the timeline to enable local areas to implement the randomisation of letters component of the trial (mid-July deadline for most areas). The delay in initiating this development of the trial has been due to changes in budgets at PHE which led to a reduction and delay in the resources that could be allocated to this project. Should the trial not gain approvals in time to implement the randomisation of letters in a participating area, we will recommend that the area use the behaviour insights informed template letter for all

schools. Such areas would be invited to trial the effect of the SMS/email reminder on uptake. In the unlikely scenario of all areas being unable to participate in the letter-intervention (due to print-deadlines being ahead of approvals), the evaluation of the new template will rely on the ecological-analysis of fidelity to the new template letter in non-trial areas and uptake. While we are and will actively work with research sites to aim for this approach, if particular areas are unhappy to universally use the new template letter, we will take the above approach using the local letter updated from last year. One of the main reasons for including a large number of research sites at this stage is to give us the greatest possibility of running an effective and sufficiently powered trial, given the practical considerations.

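### The non-trial-area letter analysis reduces gradable fidelity to similar versus dissimilar, and nothing requires the coding or the cut to be fixed before uptake is seen

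*Combined protocol and SAP*

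**What the plan says.** Section 3.10 has the letters from non-trial areas coded with the Theoretical Domains Framework and gives the purpose: "This will enable us to assess their behavioural-insight framing and fidelity to the new template letter". The analysis is then a two-group contrast. The first outcome is in "We will analyse whether those areas that used a letter similar to the new template had i) higher uptake" and the second is "ii) greater change in uptake from to last year", each "compared to areas that used a dissimilar letter".

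No section defines similar, or gives a score, a cut, a codebook, masking of the coders or a date by which coding is complete.

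Other relevant statements:

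- **Who analyses.** Section 3.10 assigns analysis to the PHE Behavioural Insights Team with the Statistics Unit. The background section says the Behavioural Insights Team designed the template together with NHS England and the PHE immunisation team. Section 5.2 says the new letter is expected to do better, while acknowledging that there is no direct evidence for this.
- **When uptake arrives.** Section 3.9 says that counts of vaccines given and denominators "will be submitted centrally at the end of November 2016, December 2016, January 2017 and February 2017", with final school-level data in March 2017.
- **What weight it carries.** Section 3.9 presents the letter review as context for understanding the trial. Section 5.1 adds that, if no area can take part in the letter randomisation, "the evaluation of the new template will rely on the ecological-analysis of fidelity to the new template letter in non-trial areas and uptake". It calls that scenario unlikely.

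**The concern.** There are two separate problems.

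The first is efficiency. Letters can share some features of the template and lack others, so fidelity comes in degrees. Sorting areas into two groups treats a letter just above the line like a full copy of the template, and one just below it like a letter with nothing in common. If uptake rises with fidelity, that wastes information in an analysis whose number of areas is limited and not under the team's control.

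The second is bias. The cut is open and the coding calls for judgement. The plan does not require either to be settled before uptake is known, and the analysing team has a stated expectation about the answer. Section 3.9 restricts who may see the interim trial analysis; the letter coding has no comparable safeguard.

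At stake is a supporting result that would be read alongside the trial or, in the Section 5.1 fallback, the only evidence on the letter.

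**Working it through.** **Figure to reproduce.** None. The documents give no number of areas, power, significance level or cut for this analysis. Everything below except the count in step 1 rests on assumptions, which are named.

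**1. Can fidelity be graded?** Table 2 has three formatting rows and seven phrasing rows: 3 + 7 = 10 features. The plan does not say that the coding yields a numeric score, but the material for one is there.

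**2. Information kept by a two-group split.** Assume a normal score with a linear relation to uptake. Splitting so that a share q lies on one side keeps φ(z_q)² / [q(1 − q)] of the information.

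| Split | φ(z_q) | Kept | Lost |
|---|---|---|---|
| 50/50 | 0.399 | 0.159/0.25 = 0.637 | 36% |
| 80/20 | 0.280 | 0.0784/0.16 = 0.490 | 51% |
| 90/10 | 0.1755 | 0.0308/0.09 = 0.342 | 66% |

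If letters fall into two clear clusters, the loss is smaller, and it vanishes when the score is truly binary.

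**3. What that means for power.** Fisher z, two-sided 0.05, assumed true correlation 0.3. The split multiplies the correlation by the square root of the share kept. For 80 areas, √(80 − 3) = 8.775:

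- graded: atanh(0.300) × 8.775 = 2.716; Φ(2.716 − 1.96) = 78%
- median split: atanh(0.239) × 8.775 = 2.142; Φ(0.182) = 57%
- 80/20: atanh(0.210) × 8.775 = 1.870; Φ(−0.090) = 46%

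The same calculation gives 47%, 32% and 25% with 40 areas, and 94%, 79% and 67% with 130.

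**4. Cut chosen after seeing uptake.** Simulation with no true association, 4,000 runs per case, 20 to 130 areas (assumed range), two-sided 0.05:

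| Choice of cut | False positives, one outcome | Either of two outcomes (assumed correlation 0.5) |
|---|---|---|
| One, fixed | 4–5% | 8–9% |
| Best of 3 | 11–13% | 19–22% |
| Best of 5 | 16–18% | 29–31% |

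About half of the one-outcome false positives favour the template. The first row shows that dichotomising at a fixed cut leaves the error rate for each outcome at its nominal level.

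**5. Unmasked coding.** Simulation with no true association, 6,000 runs per case. Coded fidelity is assumed to drift by b SD for each SD of uptake.

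| Drift b | Exposure | 40 areas | 80 areas | 130 areas |
|---|---|---|---|---|
| 0.1 | median split | 8% | 11% | 15% |
| 0.1 | graded | 10% | 14% | 20% |
| 0.2 | median split | 16% | 28% | 42% |
| 0.2 | graded | 23% | 42% | 60% |

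Hand check for b = 0.1 and 80 areas, graded: the induced correlation is 0.1/√1.01 = 0.0995, and atanh(0.0995) × 8.775 = 0.876. Then Φ(0.876 − 1.96) + Φ(−0.876 − 1.96) = 0.139 + 0.002 = 14%, in agreement.

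A graded score picks up coder drift more readily than a split does. It therefore repairs the efficiency problem but not the bias problem, which needs masking and a lock.

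**The case against.** The strongest reply is that this is contextual work. Section 5.1 makes it the sole evaluation of the letter only if all areas miss letter randomisation. If some areas miss, randomised data remain, and Section 3.7 says that one or two providers are likely to suffice for a 2% increase at all but the highest ICCs. This stands, and it limits the importance of the point.

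Several stronger readings are tempting but not supported:

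- *The letters will be coded with uptake in view.* The coding is undated, and nothing rules out finishing it before the end of November 2016. The documented gap is that no lock is required.
- *The template's designers do the coding.* No coder is named, the design was joint, and the Statistics Unit shares the analysis.
- *The two-group split itself manufactures an association.* Steps 4 and 5 place that risk in a late cut or in unmasked coding.
- *This analysis is meant to persuade areas to adopt the template.* Section 5.2 attaches that aim to the randomised trial, and the introduction to the test of the interventions.

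It is also fair to say that a raw count of Table 2 features has weaknesses. The shorter-and-simpler feature is comparative, not present or absent. The letterhead and logo feature conflicts with removing identifiers. The 2015/16 letter in Appendix 2.2 already contains close equivalents of several phrasing items, so a count may separate letters poorly. These objections affect how the score is built, not whether to grade.

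**Conclusion.** The point holds as a worthwhile, inexpensive improvement to a stated method. The two-group contrast discards about a third to a half of the information for splits between 50/50 and 80/20, if fidelity is roughly normal and related linearly to uptake; the loss is less if letters cluster. Separately, leaving coding and cut open until uptake may be known permits false-positive rates well above 5%. How far above depends on the number of areas, the score distribution and the coders' behaviour, none of which the documents give, so the figures in steps 3 to 5 show possible size and are not forecasts. Nothing in the documents shows that biased coding is planned. The consequence is modest while the letter randomisation goes ahead in at least some areas, and serious in the fallback of Section 5.1.

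**What to change.** Amend Section 3.10 as follows.

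1. Make a prespecified graded fidelity score the main exposure for both outcomes. Build it from the Table 2 features that can be judged from the letter text, with a short codebook that says what counts as present, including how near-equivalents already in last year's letters are scored. Plot uptake against the score.
2. Keep any similar/dissimilar comparison secondary, with its cut fixed in advance.
3. Code from text with area and provider identifiers removed. Record the letterhead and logo item separately before redaction, or leave it out of the score.
4. Lock the scores before the letters are linked to any 2016/17 uptake data.

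Coding by two people independently would be a sensible addition.

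The cost is a few lines of plan text, a short codebook and redaction of the letters. There are two small drawbacks. A single slope assumes equal steps per feature, which the plot helps to check. Masking may be imperfect where the wording reveals the area, but the lock still protects against coding to the 2016/17 result.

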In 2015/16 nationally, uptake in Years 1 and 2 was 53.6%.² Areas that participated in the pilot programme vaccinating primary school children (5-11 years) showed both decreasing uptake with increasing age (from 62.6% in Year 1 to 54.7% in Year 6 in 2015/16) and lower uptake last year than the previous year (57.9% compared with 60.4%). Delivery methods (school, GP or pharmacy) had considerable impact on uptake, with higher uptake in those areas that delivered flu immunisation through schoolsⁱ. Analysis has also shown that lower uptake is associated with deprivation and ethnicity.

The majority of areas offer the immunisation through school-based programmes delivered by providers that are commissioned by the NHS. Parents of eligible children are sent a letter informing them about the vaccination programme and inviting them to return the consent form for their child's vaccination. While uptake in schools is higher than GP or pharmacies, there remains approximately 30% of children for whom consent is neither given nor actively withheld.³

PHE provides template letters that immunisation providers can use. The PHE Behavioural Insights Team has worked with the NHS England and the PHE immunisation team to design the template letter for 2016/17. This letter is informed by behavioural insight theory to encourage parents to return the consent form.

There is evidence from the field of behavioural science to suggest that a low cost intervention, such as the content of an invitation letter or a reminder text message, may be effective in changing behaviour. In a previous trial run by our team, PHE Behavioural Insights Team, a 4% increase in health checks was shown by simplifying invitation letters and adding a tear-off slip where individuals could note the time and

ⁱ (55.6%, 32.9% and 16.1% uptake school, GP and pharmacy delivery respectively)

date of their first appointment, as a memory aid.⁴ Redesigning the invitation letter in combination with primer and reminder text messages increased uptake by 12% compared to the standard letter. Similar effects have been found in other non-health areas, for example, research from the Behavioural Insights Team and the DVLA showed that including an image of a person's car in their car tax collection letter increased tax payments from 40%-49%⁵ and an HMRC trial showed that providing a localised social norm message increased tax returns by 5%.⁶

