Here we set out our proposal to test whether behaviourally-informed interventions (i.e. the new template letter and SMS/email reminders) increase uptake of childhood influenza vaccination in schools, through increasing response rate. Such evidence would encourage adoption of the national template letter, which we understand many areas do not currently adopt, provide evidence for the provision of reminders and confirm whether the theory-based changes to the invitation letters have the anticipated impact.

Table 1. Target age groups for national and pilot childhood influenza immunisation programmes, by winter season.

Winter season	National programme ^a	Pilot programme ^a
2013/14	2y and 3y olds (in primary care)	4-11 year olds (reception to school year 6) eligible for vaccination in 7 geographically discrete areas.
2014/15	2-4 years of age (in primary care)	Both primary school aged children (5-11y) and secondary school aged children, 11-13y (school years 7 and 8 age) eligible for vaccination in 14 pilot areas (including pilot areas that participated in 2013/14)
2015/16	2-4 years of age (in primary care) and school years one and two (5y and 6y at 31st August)	6 pilot areas that had piloted the school based programme since 2013 to 2014 continued to offer the vaccine to all primary school age children aged 5-11 years (school years 1 to 6 age).
2016/17	2-4 years of age (in primary care) and School years 1, 2 and 3 (5, 6 and 7y at 31st August)	As in 2015/16 primary school children in years 1 to 6 in former school pilot areas will continue to be offered the vaccine.

^a Ages refer to age on 31st August/1st September of the year

2. Aims and hypothesis

The aim of this study is to investigate whether behavioural insight-informed changes to the invitation process can improve uptake of childhood flu immunisation. Our specific hypotheses are:

[figure not shown]
1. Changes to the invitation letter will increase return of consent forms and thereby increase uptake of childhood flu vaccine through schools.
2. Reminders to return the consent form will increase return of consent forms and thereby increase uptake of childhood flu vaccine through schools

3. Trial design

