5.2. Ethical issues

This study is using an intervention letter which is the nationally-available template for the childhood schools immunisation programme in the 2016/17 winter season, and by contrast using for the control arm, last year's letters. This potentially raises ethical issues given that we expect the intervention letter (which is in fact the national template) to be more effective than the control letters used last year. In conducting a trial of the letter we are randomising half of the children in participating areas to receive last year's letter. However, there is no direct evidence that the new letter will be more effective and, crucially, **we need to ensure that there is no unintentional decrease in vaccination uptake.**

Furthermore, we understand that there is often reluctance at a local level to change letters substantially from one year to the next, even given changes to the national template. A randomised trial of the new letter is the best way to obtain evidence as to whether the new letter increases uptake of vaccination. If successful, this evidence could help argue for increased fidelity to the national template by local programmes who would otherwise not change their letter.

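### The non-trial-area comparison of letters names no adjustment although areas choose their own letter, so its uptake outcome carries over any pre-existing difference; its change outcome is biased only under particular forms of selection

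*Combined protocol and SAP*

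**What the plan says.** All references are to the combined protocol and SAP.

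- **The analysis (section 3.10).** Letters from non-trial areas are graded for closeness to the new template. Two comparisons follow: "We will analyse whether those areas that used a letter similar to the new template had i) higher uptake and ii) greater change in uptake" relative to the previous year. No model, covariate, weighting, similarity cut-off or rule for conflicting results is given. Deprivation, free school meals and first language do appear in section 3.10, but for the trial's own regression models. Nothing carries them over to this comparison.
- **The letter is a local choice.** The background refers to "the national template letter, which we understand many areas do not currently adopt", and section 5.2 says "there is often reluctance at a local level to change letters substantially from one year to the next".
- **Uptake has known correlates.** The background states: "Analysis has also shown that lower uptake is associated with deprivation and ethnicity".
- **Covariates (section 3.9).** "The postcode of schools will be linked to Index of Multiple Deprivation (IMD) data to obtain a deprivation indicator", and free school meals and first language come from public sources. Ethnicity is not listed.
- **Role.** If no area can randomise letters, section 5.1 says "the evaluation of the new template will rely on the ecological-analysis of fidelity to the new template letter in non-trial areas and uptake". It calls that scenario unlikely. Otherwise, under section 3.9, this work helps to interpret the trial.
- **Cohorts (Table 1).** Outside the former pilot areas the school programme covered Years 1 and 2 in 2015/16. Year 3 joined in 2016/17.

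**The concern.** The exposure is self-selected. Areas that adopt the template may already differ in uptake from those that do not, and the background names two reasons why areas differ. A comparison of this year's uptake alone cannot separate such a difference from an effect of the letter.

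Taking the change from last year removes a stable difference. It does not remove regression to the mean, which arises if areas adopted the template because last year's uptake happened to be low (or high). The two outcomes therefore rest on different assumptions, and the plan does not say how to read them together.

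The stake is a wrong statement about the letter, in either direction, by an amount comparable with the 1 to 2 point effects considered in section 3.7 and Table 5. It is greatest if this analysis has to stand in for the randomised comparison.

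**Working it through.** The plan gives no effect size, power or error rate for this analysis, so there is no figure of its own to reproduce.

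**Inputs**

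- d: 2015/16 uptake of adopters minus non-adopters. Assumed −3 to −5 points. For scale only, the background gives 57.9% in pilot areas and 53.6% nationally for 2015/16, a gap of 57.9 − 53.6 = 4.3 points, but the year groups differ.
- r: area-level correlation between the two years. Assumed 0.7 to 0.9.
- Equal SD in both years, and no letter effect. Both assumed.
- How areas select their letter. The documents do not say, so two cases are shown.

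**Case A: a stable difference with a common trend.** Expected outcome i = d. Expected outcome ii = d − d = 0.

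**Case B: adoption depends on last year's observed uptake.** With equal SDs the regression of this year on last year has slope r. Expected outcome i = r×d. Expected outcome ii = r×d − d = −(1−r)×d.

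| d | r | A: i | A: ii | B: i | B: ii |
|---|---|---|---|---|---|
| −3 | 0.7 | −3 | 0 | −2.1 | +0.9 |
| −3 | 0.9 | −3 | 0 | −2.7 | +0.3 |
| −5 | 0.7 | −5 | 0 | −3.5 | +1.5 |
| −5 | 0.9 | −5 | 0 | −4.5 | +0.5 |

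All signs reverse if adopters were higher last year.

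**Simulation check.** This used a null letter, 100 areas, SD 8 points, r = 0.8, a logistic selection slope of 1 per SD, half of the stable variance due to deprivation, and 2,000 runs per scenario. All settings are assumed.

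- *Adoption driven by low uptake last year.* The mean gap was −6.59. The formulas predict 0.8 × (−6.59) = −5.27 for i and 0.2 × 6.59 = +1.32 for ii. The simulation gave −5.29 and +1.31. Signs were opposite in 90% of runs. The unadjusted tests rejected the true null in 93% (i) and 26% (ii) of runs. Adjusting for last year's uptake gave −0.02 points and 5.4% rejection.
- *Adoption driven by deprivation, common trend.* Outcome i was −4.14 and ii was 0.00. Signs were opposite in 49% of runs, which is chance. Adjusting for last year's uptake alone left −0.90 points; adding deprivation brought this to −0.02.
- *No selection.* Opposite signs are expected by chance in about 40% of cases at r = 0.8.

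So outcome i needs both last year's uptake and deprivation as covariates. Neither the adjusted level nor the change is safe under every form of selection.

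**The case against.** The strongest reply is that section 3.10 is silent on adjustment rather than opposed to it, and that this is a supporting, openly ecological analysis. Four stronger readings might be inferred, and the documents do not support them.

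- *That the plan has chosen an unadjusted analysis.* It has not said so. The point concerns what follows if the text is carried out as it stands. Outcome ii also uses last year's uptake already, as a change score.
- *That i and ii will systematically point in opposite directions.* This needs adoption to depend on last year's observed uptake. No section says it does; the one reason given for keeping a letter is local reluctance to change it. With a stable difference such as deprivation and a common trend, ii is centred on zero.
- *That the bias in ii is as large as the effects the trial is planned around.* Three of the four Case B values (+0.3, +0.5, +0.9) are below 1 point.
- *That baseline adjustment is always better than change.* If adoption follows a stable factor that is not measured, the adjusted level stays biased while the change does not.

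It is also fair that reporting both outcomes is partly self-revealing: on the same areas and year groups, i minus ii equals the baseline gap (for example −3.5 − 1.5 = −5).

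What stands is that the letter is self-selected, uptake has known correlates, and no adjustment is planned for outcome i.

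**Conclusion.** The point holds in a limited form and should be acted on. Taken as written, outcome i is confounded by any earlier difference in uptake between adopters and non-adopters. Under the assumed ranges the carry-over is −3 to −5 points if the difference is stable and −2.1 to −4.5 points if adoption follows last year's uptake. Outcome ii is near zero in the first case with common trends, and off by +0.3 to +1.5 points in the second. The gap, the correlation, equal SDs and the selection mechanism are all assumptions, and the direction reverses if adopters started higher.

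The practical weight is moderate. A reader might take section 5.1 to mean that the evaluation of the letter generally rests on this analysis. It does so only if no area can randomise letters; in every other case the randomised comparison carries the conclusion.

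**What to change.** Before the final data arrive in March 2017, amend section 3.10 as follows.

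1. Replace unadjusted outcome i with 2016/17 uptake adjusted for 2015/16 uptake, IMD or free school meals, and the proportion of children whose first language is not English. The last is a proxy, because ethnicity is not among the listed variables. Analyse at the level that chose the letter.
2. Add the same deprivation and language covariates to outcome ii. This addresses trends that differ with those factors; it does not remove regression to the mean.
3. Use comparable year groups in both years: Years 1 and 2 outside the former pilot areas.
4. Report the adjusted level and the change side by side, state the assumption behind each, and label both observational. Draw a conclusion about the letter only if they agree in direction. Agreement is a minimum condition, not proof, since only measured factors are covered.

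The cost is SAP wording and a few covariates. Outcome ii already needs 2015/16 uptake, and the school characteristics are public. Section 3.9 does not say explicitly that the linkage extends to non-trial areas, so that should be confirmed. Units without 2015/16 uptake drop out of the adjusted model, as they already would for outcome ii.
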